## ***Varenicline for the Treatment of DSM 5 Cannabis Use Disorder in Adults***

### **Study Overview and Design**

Although cannabis use is widespread and basic science research on cannabinoids is well-developed, advancements in medication development for cannabis use disorder (CUD) have been limited. Varenicline, a selective nicotinic nACh receptor partial agonist of the  $\alpha 4\beta 2$  subtype and a full agonist of the  $\alpha 7$  subtype, is arguably the most effective pharmacotherapy for promoting tobacco abstinence, and has also shown promise for the treatment of alcohol use disorder. Varenicline may improve cannabis use outcomes through multiple mechanisms, including interaction with the mesolimbic dopamine system, enhancement of cognitive functioning, and restoration of inhibitory control. To date, however, varenicline has not been evaluated in individuals specifically seeking treatment for CUD. Through the UG3/UH3 mechanism we proposed to rapidly yet thoroughly assess the utility of varenicline for CUD to potentially advance varenicline through the FDA's drug development approval pipeline. In the UG3 component, we conducted a six-week, placebo-controlled proof-of-concept clinical trial of varenicline for CUD, paired with pre- and post-evaluations of cognitive functioning and neural circuitry involved in cannabis cue reactivity and inhibitory control to elucidate the pharmacodynamics of varenicline as a treatment for CUD. We successfully met the pre-specified Go/No Go criteria for the UG3 study. For the the UH3 component, we will extend our promising UG3 findings by conducting a 12-week, placebo-controlled, double-blind trial to determine the impact of varenicline on cannabis use outcomes.

**Specific Aim 1.** To evaluate the efficacy of varenicline for cannabis use disorder (CUD). **Hypothesis 1:** A 12-week treatment course of varenicline, compared to placebo, for CUD will yield significant reduction in cannabis use.

**Specific Aim 2.** To examine the safety and tolerability of varenicline, compared with placebo, when used for CUD. **Hypothesis 2:** A 12-week treatment course of varenicline, compared to placebo, will demonstrate adequate safety and tolerability, as defined by non-inferiority in the frequency of treatment-emergent adverse events.

**Exploratory Aim.** To evaluate the effect of varenicline on negative affect, and the relationship between negative affect and cannabis use reduction, during CUD treatment. **Exploratory Hypothesis 1:** A 12-week treatment course of varenicline, compared to placebo, for CUD will yield reduction in negative affect. **Exploratory Hypothesis 2:** Reduction in negative affect during varenicline treatment will be associated with cannabis use reduction.

**Participants.** A total of approximately180 participants with CUD, aged 18 and over, will be recruited over a 32-month period at 2 participating sites.

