detection cut-off value of 30.00 ng/ml (Abbott AXSSYM® System package insert). Urine creatinine will also be obtained, as creatinine normalization has been proposed as a method to differentiate new cannabis use from residual drug excretion (Huestis and Cone, 1998; Schwilke et al, 2011). **Urine Cotinine:** Nicotine is metabolized to cotinine by the liver. Cotinine has a longer half-life than nicotine, and thus serves as a more reliable biomarker of cigarette smoking (Zevin et al., 2000). Urine will be screened qualitatively at each visit (detection cut-off value of 200 ng/ml). **Marijuana Craving Questionnaire (MCQ):** The MCQ (Heishman et al, 2001) is a Likert-based self-assessment of cannabis craving shown to be a valid and reliable instrument for measuring cannabis craving. The 12-item MCQ will be used, which has been constructed by selecting the three items from each factor of the full 47-item MCQ that exhibited the most within-factor reliability (Heishman et al, 2009). **Cannabis Withdrawal Scale:** The Cannabis Withdrawal Scale (Allsop et al, 2011) is comprised of 19 items for which participants rate severity of symptoms in the previous 24 hours. **Marijuana Use Summary Sheet/Self-Efficacy Questionnaire/Marijuana Problem Scale/Reasons for Quitting Questionnaire:** These worksheets, created by Stephens and colleagues (2000), will be used to gather information from participants to prepare personalized feedback reports (PFRs) for use in the motivational enhancement sessions. **DSM-5 Criteria for CUD:** DSM-5 criteria will be assessed at four time points to determine changes in severity of cannabis use disorder.

**Safety Assessment. Review of Adverse Events:** Adverse events (AEs) will be assessed weekly by study personnel. The type of AE, severity of AE, and the relationship to study medication will be recorded. AEs will be coded on a weekly basis using Medical Dictionary for Regulatory Activities (MedDRA) rules.

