impact on parameter inference, thus when detected, a negative binomial distribution will be specified and model fit will be compared to the Poisson model. An offset variable will be included in the models to account for possible differences in between visit timing. Models will be computed both adjusted for design variables and for significant covariates and confounders found in the preliminary analysis. Working correlation structures will be independently compared using the quasi-likelihood under the independence model criterion statistic (QIC). Model based means will be used to construct the pairwise comparisons between groups. All design adjusted models will include baseline average use sessions, study visit, treatment group assignment and randomization stratification variables (smoking status and gender). Additional exploratory approaches (e.g., analysis excluding participants with <80% medication adherence, per protocol analysis, completers analysis) will be undertaken.

**Specific Aim 2:** We will also compare the frequency of treatment-emergent AEs between treatment groups using a non-inferiority analysis. Of particular interest will be AEs leading to medication discontinuation and the occurrence of treatment-related serious AEs (SAEs). We will specifically compare neuropsychiatric AEs and suicidality (C-SSRS) ratings by treatment group. We hypothesize that treatment with varenicline will not cause undue adverse events and will be non-inferior to the placebo group by a margin ( $\delta$ ) of no more than a 10% using the Farrington-Manning score test for non-inferiority.

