substance use report logs. We anticipate the increased information will allow better precision in the estimated effect between randomized study groups. Assuming this, coupled with the more extended 12-week treatment compared with the truncated treatment phase in the prior UG3 proof-of-concept trial, results in a slightly increased effect size of  $d=0.5$ , a high correlation between measures taken over time on the same participant ( $p=0.95$ ) and a 5% type 1 error rate, 57 participants are necessary in each treatment arm to achieve adequate power (80%). Additionally, the UG3 noted a higher than expected attrition rate of 35%, thus we anticipate that, despite our best efforts and revised approach, attrition during the study could reach 35%. Thus to ensure that we have the appropriate sample, we will enroll and randomize **approximately 90 participants per group for a total sample size of approximately n=180**. This will allow us to detect a difference in cannabis use session of at *least*  $d=0.5$  between randomized study groups while accounting for up to 35% study attrition. Similar to adult varenicline phase III studies (Gonzales et al., 2006), for the primary safety analysis we will compare the frequency of all treatment-emergent AEs (defined as any AE occurring between treatment initiation and one week following treatment conclusion), SAE's between varenicline and placebo groups. A non-inferiority analysis will be utilized (Piaggio et al., 2006). With an estimated placebo treatment-emergent AE rate of 75% (Gonzales et al., 2006), 90% power and two sided  $\alpha = 0.05$ , within our proposed sample of **approximately 180 randomized participants** we will be able to detect a 10% non-inferiority margin in AE frequency between treatment groups if it exists.

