### ***b. Sources of Materials***

Research material obtained from individual participants includes questionnaires and in-person and remote interviews with study personnel, and blood and urine samples. To ensure confidentiality, all participant data will be letter/number coded, and only the investigators will have access to the master lists of codes. The research material will be obtained specifically for research purposes. Written research material obtained will be stored in the Addiction Sciences Division at MUSC or at Behavioral Health Services of Pickens County in Pickens, SC, in an office that is locked when not in use. Urine samples from MUSC site will be stored in the Clinical Neurobiology

Urine samples from the Pickens site will be stored at Behavioral Health Services of Pickens County and then sent to MUSC CNL for analysis in batches.

*c. Potential Risks*

The varenicline package insert details adverse events associated with the medication. Specifically, it reports that "the most common adverse reactions (>5% and twice the rate seen in placebo-treated patients) were nausea, abnormal (e.g., vivid, unusual, or strange) dreams, constipation, flatulence, and vomiting." Meta-analyses of the four main adverse events in varenicline versus placebo groups in adult trials yielded relative risks (RRs) of 3.21 (95% CI 2.71, 3.80) for nausea, 1.50 (95% CI 1.26, 1.79) for insomnia, 2.79 (95% CI 2.09, 3.72) for abnormal dreams, and 1.20 (95% CI 1.00, 1.45) for headache (Cahill et al., 2009). While post-marketing anecdotal reports of psychiatric adverse events led to an FDA "black box" warning for varenicline, a reanalysis of controlled trials revealed no evidence that varenicline is associated with neuropsychiatric adverse events (Thomas et al., 2015). There is a potential risk of loss of confidentiality.

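### Hypothesis 2 defines tolerability by one pooled any-AE non-inferiority test, and neither a pass nor a failure on that test would answer Aim 2

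*Combined protocol and SAP*

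**What the plan says.** The Study Overview and Design section, under Specific Aim 2, states that 12 weeks of varenicline "will demonstrate adequate safety and tolerability, as defined by non-inferiority in the frequency of treatment-emergent adverse events". Non-inferiority in AE frequency is thus the definition of adequate tolerability, not one piece of evidence for it.

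The Statistical Analysis section gives the mechanics. Under Specific Aim 2, varenicline "will be non-inferior to the placebo group by a margin" of at most 10%, by the Farrington-Manning score test. Under Power and Sample Size, the plan says that "we will compare the frequency of all treatment-emergent AEs", a treatment-emergent AE being "any AE occurring between treatment initiation and one week following treatment conclusion". The planning figure is introduced by "With an estimated placebo treatment-emergent AE rate of 75" per cent, and about 180 randomized participants are said to give 90% power at a two-sided 5% level.

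The same section singles out AEs that lead to stopping the medication and treatment-related serious AEs. It also plans to compare neuropsychiatric AEs and C-SSRS ratings by group. None of these has a margin or decision rule, and none enters the definition in Hypothesis 2.

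Under Potential Risks, the protocol reports that adult trials "yielded relative risks (RRs) of 3.21 (95% CI 2.71, 3.80) for nausea", with 2.79 for abnormal dreams, 1.50 for insomnia and 1.20 for headache. It gives no placebo rates for these events. On data capture, the Safety Assessment paragraph says: "The type of AE, severity of AE, and the relationship to study medication will be recorded".

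**The concern.** The endpoint is close to its ceiling before the drug has any effect. With three in four placebo participants expected to report something over about 13 weeks, an AE caused by varenicline counts only if it falls in someone who would otherwise have reported nothing. A minor cold counts the same as vomiting that ends treatment.

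The protocol already names the events on which varenicline is expected to be less well tolerated, and then defines tolerability by a measure that dilutes them. What is at stake is whether Aim 2 can be answered. A pass would not show that the drug is well tolerated on the events that matter. A failure would not show that it is poorly tolerated.

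**Working it through.** **Inputs from the documents.** Placebo any-AE rate 75%, margin 10% (read as percentage points), two-sided alpha 0.05 (one-sided 0.025), about 90 per arm, and relative risks (RR) of 3.21, 2.79, 1.50 and 1.20.

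**Assumptions.** Frequency means the proportion with at least one AE. Event types are independent. Placebo rates for single events are not in the documents and are varied.

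**1. The plan's own figure.** With 75% in both arms, the number per arm for 90% power is

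(1.960 + 1.282)² × (2 × 0.75 × 0.25) / 0.10² = 394.03, or 395 after rounding up (unrounded normal quantiles).

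At 90 per arm the standard error is √(0.375/90) = 0.0645. Power is Φ(0.10/0.0645 − 1.960) = Φ(−0.41) = 34%. Exact enumeration of the Farrington-Manning test also gives 34% (46% at one-sided 0.05). The stated 90% is not reproduced.

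**2. Dilution.** If p is the placebo rate of an event, then

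any-AE rate on varenicline = 1 − 0.25 × Π[(1 − RR·p)/(1 − p)].

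Example: placebo nausea 10%, varenicline 32.1%. The any-AE rate is 1 − 0.25 × (0.679/0.900) = 81.1%. So 22.1 extra points of nausea become 6.1 extra any-AE points.

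The last column is the probability that the test declares non-inferiority at 90 per arm, one-sided 0.025, by enumeration.

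| Assumed placebo rates | Extra nausea (points) | Any-AE on varenicline | Extra any-AE (points) | Test passes |
|---|---|---|---|---|
| Identical arms | 0 | 75.0% | 0 | 34% |
| Nausea only, 5% | 11.1 | 77.9% | 2.9 | 20% |
| Nausea only, 8% | 17.7 | 79.8% | 4.8 | 13% |
| Nausea only, 10% | 22.1 | 81.1% | 6.1 | 9% |
| All four*, 5/5/3/5% | 11.1 | 79.9% | 4.9 | 13% |
| All four*, 5/8/3/8% | 11.1 | 80.4% | 5.4 | 11% |
| All four*, 8/12/5/12% | 17.7 | 83.4% | 8.4 | 4.4% |
| All four*, 10/13/6/13% | 22.1 | 85.0% | 10.0 | 2.5% |
| All four*, 15/15/8/15% | 33.1 | 88.7% | 13.7 | 0.5% |

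*Order: nausea, insomnia, abnormal dreams, headache.

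**3. Where the margin is crossed.** Nausea alone reaches 10 any-AE points at a placebo nausea rate of about 15.3% under independence. If instead all excess nausea fell in otherwise AE-free participants, the crossing would be at 0.10/2.21 = 4.5%.

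**4. What a pass needs.** With 68 of 90 placebo participants reporting an AE, varenicline must have 65 or fewer, an observed difference of −3/90 = −3.3 points. Varenicline has to look better than placebo.

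**5. Would a larger trial cure it?** Take 395 per arm and the nausea-only case at 5%. The standard error is √[(0.75 × 0.25 + 0.779 × 0.221)/395] = 0.0302. The pass probability is Φ((0.10 − 0.029)/0.0302 − 1.960) = Φ(0.39), about 65%. A correctly sized trial would therefore usually pass while nausea rose from 5% to 16%. The endpoint fault is separate from the power fault.

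**The case against.** **A false pass is unlikely at this size.** A reader might infer that the trial would probably declare varenicline well tolerated despite tripled nausea. The plan's figures do not support that. A true excess inside the margin is not a demonstration of non-inferiority, which needs the upper confidence limit below the margin. The scenarios with excess events pass at most about 20% of the time, and the likely result is inconclusive. This objection stands, and the point is limited accordingly.

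**The cited excesses need not stay inside the margin.** A reader might also infer that they mostly would. That depends on placebo rates that the documents do not give, and on independence. The four-event total runs from 4.9 to 13.7 points over the range shown, and other dependence could make it smaller or larger. This also stands.

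**Other safety comparisons are planned.** Aim 2 is to examine safety and tolerability. The plan compares discontinuations due to AEs, serious AEs, neuropsychiatric AEs and C-SSRS ratings, and it records type and severity. So the trial will not ignore these matters. What remains is that none of them bears on the conclusion as Hypothesis 2 defines it, and that the common expected events are not named for individual comparison.

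**Any-AE proportion is an inference.** The documents say frequency. A 75% rate tested with a two-proportion score test makes the per-participant proportion the natural reading, but it is not stated outright.

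**Intervals without a margin give no pass/fail rule.** This is fair, and is a reason to keep the existing test as one component.

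**Conclusion.** The concern holds in a limited form. Hypothesis 2 rests adequate safety and tolerability on one pooled endpoint that, at 75% on placebo, responds only in the remaining 25% and carries no information on type, severity or discontinuation. Under independence and an assumed placebo nausea rate of 5% to 10%, 11 to 22 extra points of nausea shrink to about 3 to 6 any-AE points. Whether the four cited events together cross the margin cannot be settled from the documents.

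At 90 per arm the test passes about 34% of the time with no difference at all. A failure therefore says little about poor tolerability, and dilution means that a pass says little about good tolerability. The defect is that neither result answers Aim 2, not that a misleading pass is likely. It should be corrected, because it changes what Aim 2 can conclude and the data needed are already collected.

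**What to change.** Amend Hypothesis 2, the Specific Aim 2 analysis and the Power and Sample Size paragraph as follows.

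- State that the endpoint is the proportion of participants with at least one treatment-emergent AE.
- Keep the Farrington-Manning comparison, and state that by itself it neither establishes nor refutes adequate tolerability.
- Pre-specify, alongside it, between-arm risk differences with 95% confidence intervals for AEs leading to study-drug discontinuation, for moderate or severe AEs, and for nausea, abnormal dreams, insomnia and headache individually.
- Base the tolerability conclusion on these results taken together.
- Correct the power statement for the any-AE test.

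The cost is protocol and SAP wording. Type, severity and relationship to study medication are already recorded weekly, so no new data or procedures are needed. The downside is small: the conclusion would rest on several estimates, some of them imprecise for rarer events, rather than on one pass/fail test.

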### **Inclusion Criteria**

- Meet DSM-5 criteria for cannabis use disorder and use cannabis at least 3 days per week in the last 30 days.
- Express interest in receiving treatment for cannabis use disorder and reducing use.
- Males and females at least 18 years of age.
- If female and of childbearing potential, must agree to use acceptable methods of birth control for the duration of the trial.
- Must consent to random assignment, and be willing to commit to medication ingestion.
- Must be able to read and provide informed consent.
- Must have body weight  $>110$ lbs (50kg) and have BMI between 18 and 35  $\text{kg}/\text{m}^2$
- Must function at an intellectual level and have knowledge of the English language to sufficiently allow for accurate completion of assessments.

### **Exclusion Criteria**

- Women who are pregnant, nursing, or plan to become pregnant during the course of the study.

- Individuals with severe renal impairment (creatinine clearance less than 30 mL per minute).
- Lifetime history of DSM-5 Bipolar I or II Disorder, Schizophrenia or other psychotic disorder. Stably treated MDD, Dysthymia, GAD, Social Phobia, and Specific Phobia diagnoses are acceptable (i.e. same dose of medication has been prescribed for at least 2 months prior to screening and no changes in current medication expected during course of the trial).
- Past year or current posttraumatic stress disorder.
- Subjects who are actively suicidal, or who report suicidal ideation (SI) with intent or plan in the past year.
- Subjects who have a SBQ-R total score  $\geq 8$ , or for whom the investigator judges that a risk assessment by a qualified medical professional is required. Subjects answering 'yes' on questions 4 or 5 of C-SSRS will be referred to assessment by a qualified mental health professional.
- Suicidal behavior within the past 10 years or a lifetime history of serious or recurrent suicidal behavior.
- Subjects who are believed to be at homicidal risk.
- Concomitant use of psychotropic medications, with the exception of stable doses (defined as no dosing adjustments in the past two months) of non-MAO-I antidepressants, non-benzodiazepine anxiolytics, and ADHD medications.
- Current use of medications prescribed for mania or psychosis.
- Current use of bupropion or nortriptyline.
- Moderate or severe non-cannabis substance use disorders within the past 60 days with the exception of tobacco use disorder.
- Past year or current moderate or severe alcohol use disorder.
- Individuals taking an investigational agent within the last 30 days before baseline visit.
- Individuals with clinically significant medical disorders or lab abnormalities.
- Any individual at screening with SGOT (AST) or SGPT (ALT) greater than 3 times the upper limit of normal and/or total bilirubin greater than two times the upper limit of normal.
- Individuals with clinically significant cardiovascular disease in the past 6 months (e.g., myocardial infarction, CABG, PTCA, severe or unstable angina, serious arrhythmia, or any clinically significant ECG conduction abnormality)
- Individuals with clinically significant cerebrovascular disease in the past 6 months such as TIA, CVA, or stroke
- Hypersensitivity to varenicline.
- Individuals who have participated in the clinical trial of any investigational agent within the last 60 days.
- Individuals who are on probation or under a mandate to obtain treatment.
- Individuals with plans to initiate or change frequency of attendance at self-help meetings (e.g. AA, NA).

**Recruitment.** Recruitment is planned to occur through both clinical referral and advertising.

**Procedures.**

Strategies to Ensure a Robust and Unbiased Approach: As detailed throughout this section, the proposed study will achieve robust and unbiased results via several design features including: explicit inclusion/exclusion criteria; randomization of treatment condition; placebo control; blinding; use of validated measures and methods; explicit hypotheses and corresponding planned statistical analyses; power estimates; planned handling of retention/attrition and missing data; objective adherence monitoring; and careful consideration of potential confounds.

Screening and Eligibility Assessment. Individuals will be screened by the research study intake coordinator. The consent and all screening/eligibility procedures may be completed remotely, via a secure Web-based platform such as Doxy.me or RedCap, or a combination of these platforms as appropriate. A quick screen, focused on inclusion/exclusion psychiatric diagnoses, medical status, current medication regimen, and ability and willingness to commit to completion of study procedures, will be used to initially determine study eligibility. Interested individuals will be given a full description of the study procedures and asked to read and sign an IRB-approved informed consent form. In order to confirm and document understanding, individuals will be asked to

complete a consent quiz prior to signing the form. They will also be asked to complete a W9 during the informed consent/teleconsent process.

Diagnostic/Descriptive Assessment. The MINI International Neuropsychiatric Interview (MINI) will be used to assess psychiatric and substance use diagnoses. A detailed medical history will be taken, and subjects will be asked to complete bloodwork at the MUSC CNL or a local LabCorp of their choosing (or AnMed lab in Pickens) to ensure the individual is eligible to participate. A physical exam will be conducted only if there is an issue raised by either the medical history or bloodwork. In the event that an individual is found to be ineligible to participate in this research protocol, he or she will be given an appropriate referral for further medical care or to an appropriate treatment program.

Treatment Assignment. Individuals who meet all inclusion criteria and no exclusion criteria will be randomized to receive either varenicline or matching placebo. Randomization (stratified on tobacco smoking status and gender) and dispensing will be performed by the MUSC Investigational Drug Service. Varenicline will be provided at the standard recommended dose of 0.5mg daily for three days, then 0.5mg twice daily for four days, and then 1mg twice daily for the remainder of the 12-week treatment period. Matching placebo and varenicline (0.5mg and 1mg) capsules will be compounded by IDS utilizing Letco 00 capsules and microcrystalline cellulose filler. For the Pickens site, medication will be packaged and dispensed by MUSC IDS, and then shipped to Pickens via registered courier. On site, medication will be stored in a controlled access environment and provided to participants by appropriately trained and designated study staff, with double checks in place. In extenuating or emergency circumstances, when patient visits are not feasible or are prohibited, such as in the case of a pandemic, weekly medication may be mailed to participants.

Medication Management. Medication Management (MM) is a common-sense, generalizable approach to encourage adherence to medication specifically, and to a treatment plan in general. Once a week, participants will be seen for a brief MM session. Sessions will be focused on (a) developing and maintaining rapport, (b) reviewing AEs and concomitant medications, and (c) discussing progress with medication adherence and cannabis reduction/abstinence. These sessions provide an opportunity to address challenges and help participants devise strategies for success. A similar intervention was utilized in the NIDA-funded CTN0053 trial (Achieving Cannabis Cessation—Evaluating N-Acetylcysteine Treatment) to provide an evidence-based treatment platform for all participants. MM with participants at the Pickens site will be done by approved medical personnel there and, as needed, by MUSC site medical personnel via WebEx or Doxy.me, HIPAA-compliant, MUSC Information Security-approved platforms for telehealth. In extenuating or emergency circumstances, when patient visits are not feasible, safe, or are prohibited, such as in the case of a pandemic, MM at both sites may be completed remotely by telehealth/phone.

Assessments. **Table 4** provides an overview of assessments; a brief description of the instruments is provided below. In extenuating or emergency circumstances, when patient visits are not feasible, safe, or are prohibited, such as in the case of a pandemic, visits and their procedures that can be completed remotely by telehealth/phone may be. Additionally, urine drug and cotinine tests may be completed less than weekly if deemed appropriate. All of the assessments will mirror what would be done in clinic, and as such do not add risk to the participants.

